*Radioactive Drug Research Committee (RDRC)	Approval Date:
VNHH-Radiation Safety Committee (YNHH-RSC)	Approval Date:
Yale University RSC (YU-RSC)	Approval Date:
Magnetic Resonance Research Center PRC (MRRC-PRC)	Approval Date:
*Nursing Research Committee	Approval Date:
YSM/YNHH Cancer Data Repository (CaDR)	Approval Date:
Dept. of Lab Medicine request for services or specimens for	m

Imaging on YNHH Diagnostic Radiology equipment request form (YDRCTO request) found at http://radiology.yale.edu/research/ClinTrials.aspx)

*Approval from these committees is required before final HIC approval is granted. See instructions for documents required for initial submission and approval of the protocol. Allow sufficient time for these requests. Check with the oversight body for their time requirements.

2. **Probable Duration of Project:** State the expected duration of the project, including all follow-up and data analysis activities. 7 years

3.	Research Type/Phase: (Check all that apply)
	a. Study Type
	Single Center Study
	Multi-Center Study
	Does the Yale PI serve as the PI of the multi-site study? Yes No
	Coordinating Center/Data Management
	Other:
	b. Study Phase N/A
	Other (Specify)

- 4. Area of Research: (Check all that apply) Note that these are overlapping definitions and more than one category may apply to your research protocol. Definitions for the following can be found in the instructions section 4c:
 - Clinical Research: Patient-Oriented Clinical Research: Outcomes and Health Services

Page **3** of **51**

Translational Research #1 ("Bench-to-Bedside")
 Interdisciplinary Research
 Translational Research #2 ("Bedside-to-Community")
 Community-Based Research

5. Is this study a clinical trial? Yes \square No \square

NOTE the current ICMJE (International Committee of Medical Journal Editors) definition of a clinical trial: "any research study that prospectively assigns human participants or groups of humans to one or more health-related interventions to evaluate the effects on health outcomes." Health-related interventions include any intervention used to modify a biomedical or health-related outcome (for example, drugs, surgical procedures, devices, behavioral treatments, dietary interventions, and process-of-care changes). Health outcomes include any biomedical or health-related measures obtained in patients or participants, including pharmacokinetic measures and adverse events" If yes, where is it registered?

Clinical Trials.gov registry \square Other (*Specify*)

Registration of clinical trials at their initiation is required by the FDA, NIH and by the ICMJE.

If this study is registered on clinicaltrials.gov, there is new language in the consent form and compound authorization that should be used.

For more information on registering clinical trials, including whether your trial must be registered, see the YCCI webpage, http://ycci.yale.edu/researchers/ors/registerstudy.aspx or contact YCCI at [contact])

6. Does the Clinical Trials Agreement (CTA) require compliance with ICH GCP (E6)? Yes No N/A

7. Will this study have a billable service? A billable service is defined as any service rendered to a study subject that, if he/she was not on a study, would normally generate a bill from either Yale-New Haven Hospital or Yale Medical Group to the patient or the patient's insurer. The service may or may not be performed by the research staff on your study, but may be provided by professionals within either Yale-New Haven Hospital or Yale Medical Group (examples include x-rays, MRIs, CT scans, specimens sent to central labs, or specimens sent to pathology). Notes: 1. There is no distinction made whether the service is paid for by the subject or their insurance (Standard of Care) or by the study's funding mechanism (Research Sponsored). 2. This generally includes new services or orders placed in EPIC for research subjects.

Yes 🗌 No🖂

If answered, "yes", this study will need to be set up in OnCore, Yale's clinical research management system, for Epic to appropriately route research related charges. Please contact [contact]

APPROVED BY THE YALE UNIVERSITY IRB 10/25/2023

8.. Are there any procedures involved in this protocol that will be performed at YNHH or one of its affiliated entities? Yes No X_ If Yes, please answer questions a through c and note instructions below. If No, proceed to Section III.

a. Does your YNHH privilege delineation currently include the **specific procedure** that you will perform?

b. Will you be using any new equipment or equipment that you have not used in the past for this procedure?

c. Will a novel approach using existing equipment be applied?

If you answered "no" to question 8a, or "yes" to question 8b or c, please contact the YNHH Department of Physician Services ([name]) for prior approval before commencing with your research protocol.

- I have read a copy of the protocol and approve it being conducted at YNHH.
- I agree to notify the IRB if I am aware of any real or apparent institutional conflict of interest.
- The principal investigator of this study is qualified to serve as P.I. and has the support of the hospital for this research project.

YNHH HSPA Name (PRINT) and Signature

Date

Date

SECTION IV: RESEARCH PLAN

1. **Statement of Purpose:** State the scientific aim(s) of the study, or the hypotheses to be tested.

Our project has two overarching goals. 1) We will use newly developed positron emission tomography (PET) technology to investigate the dopaminergic neurochemistry of drugs of abuse including marijuana, traditional cigarettes, and 2) We will extend our PET technology to an additional neurotransmitter system – namely, the opioid-ergic system, using the same drugs of abuse.

The majority of the research investigating the neurochemical mechanisms involved in drug addiction has been conducted in animals. From these studies it is well known that the mesolimbic dopamine (DA) system drives the reinforcing effects of drugs of abuse. In particular, a seminal study demonstrated that DA is released (in animals) by all drugs that are abused by

Page 8 of 51

humans¹. In addition, it has been hypothesized that DA influences reward "wanting", while the opioid system governs reward "liking"², both of which are critical for understanding neurochemical processes underlying compulsive drug use. These findings in animals need to be confirmed in humans to validate the animal models, to improve our understanding of the neurochemistry of drug abuse, and so that we can test new medications in humans. With PET we can noninvasively, and now dynamically, measure neurotransmitter changes in response to drugs of abuse in humans. This investigation will utilize a system previously developed by our group for imaging and modeling DA release in humans from cigarette smoking in the PET scanner. Our experimental and analytical techniques are sensitive enough to detect moderate increases in striatal DA (in magnitude and spatial extent) that are expected with marijuana. Our model is also uniquely able to capture the *temporal profile* of *brief* DA responses. The goals of this study are to extend our paradigm to additional drugs of abuse (marijuana) and to extend our technology to an additional neurotransmitter system (opioid-ergic) with the same drugs of abuse (tobacco, marijuana). This will allow us to determine the spatio-temporal patterns of combined DA and beta-endorphin fluctuations associated with drugs of abuse in the living human brain.

Aim 1: To examine the magnitude, location and timing of drug-induced dopamine release.

- **a.** Tobacco smokers (n=20) will be imaged with [¹¹C]raclopride PET, after overnight abstinence from tobacco. Subjects will smoke their preferred brand of cigarette during the PET scan.
- **b.** Marijuana smokers (n=20) will be imaged with [¹¹C]raclopride PET, after overnight abstinence from marijuana. Subjects will smoke a marijuana cigarette during the PET scan.

Aim 2: To examine the magnitude, location and timing of drug-induced beta-endorphin release. *We will attempt to use the same subjects from Aim 1 for Aim 2 (Marijuana Exposed Healthy Controls are the exception)

- **a.** Tobacco smokers (n=20) will be imaged with [¹¹C]carfentanil PET, after overnight abstinence from tobacco smoking. Subjects will smoke their preferred brand of cigarette before or during the drug condition PET scan.
- **b.** Marijuana smokers and Marijuana Exposed Healthy Controls (n=20) will be imaged with [¹¹C]carfentanil PET, after overnight abstinence from marijuana smoking. Subjects will smoke a marijuana cigarette before or during the drug condition PET scan.

Aim 3: To examine the magnitude, location and timing of marijuana-induced dynorphin release. Cannabis has diverse effects on the endogenous opioid system. We will image Marijuana Smokers and Marijuana Exposed Healthy Controls (n=20) with [¹¹C]EKAP PET, after overnight abstinence from marijuana smoking. Subjects will smoke a marijuana cigarette before or during the drug condition PET scan.

2. **Background:** Describe the background information that led to the plan for this project. Provide references to support the expectation of obtaining useful scientific data.

Page 9 of 51

The neurochemistry of drug addiction. Drug addiction is a widespread public health issue, affecting at least one quarter of the adult U.S. population. A key process of chronic drug use is the transition from voluntary to compulsive use in spite of adverse consequences. The rewarding aspects of drug abuse are known to be critical to both the initiation, i.e., voluntary, and maintenance of drug use⁴. Reward processes are primarily influenced by the DA and opioid neurotransmitter systems. It has been hypothesized that DA influences reward "wanting", while the opioid system governs reward "liking"², both of which are critical for understanding neurochemical processes underlying compulsive drug use. For example, initial drug seeking for the pleasurable aspects of the drug ("liking") often gives way to habitual drug use ("wanting"), particularly in response to drug cues, despite individuals reporting little pleasure from the drug itself⁵. While much preclinical work has studied dopamine-opioid interactions in reward response^{6,7}, extending this work to study the neurochemistry of reward response in *clinical* substance abuse disorders has been limited.

Using PET to study to neurochemistry of drug addiction. PET neuroreceptor imaging has revealed a wealth of *in vivo* research examining *basal* levels of dopaminergic and opioid receptor availability in substance abuse disorders. In other words, these studies ask the question, "*In the absence of drug administration, how many receptors are available for radioligand binding*?" Using these methods, lower dopamine D₂/D₃ receptor availability in drug users compared to healthy controls has been identified as a key hallmark of substance abuse disorders, and this currently influences therapeutics development^{8,9}. In contrast, different substances have diverse effects on the opioid system. Reduced µ-opioid receptor availability in smoking¹⁰ and nicotine dependence severity^{11,12}, while increased µ-opioid receptor availability was associated with chronic cocaine use¹³⁻¹⁶, heroin dependence^{17,18}, alcohol dependence¹⁹⁻²¹, and alcohol craving²¹⁻²³. Different drugs of abuse may thus affect the opioid receptors in a variety of ways, underscoring the importance of studying the opioid system in substance abuse disorders.

To build on these findings, many groups have attempted to use PET neuroreceptor imaging to examine the acute drug response of the dopamine and opioid systems *in vivo*. These studies are designed to ask the question, *"How does the number of receptors available for radioligand binding change after drug administration?"* The common methodology for these experiments is to use two PET scans to measure the neurotransmitter response, inferred by changes in radioligand binding, following drug administration. First, a baseline PET scan is acquired to measure the available receptors indexed by binding potential (BP). Next, the drug is administered, followed by a second PET scan acquired to measure the post-drug BP. If the drug leads to neurotransmitter release, the additional neurotransmitter will bind to the receptor site, decreasing the number of available receptors for radioligand binding (and BP). Measured changes in BP (baseline BP minus post-drug BP) thus enable an indirect measure of neurotransmitter increase. This two-scan paradigm has been used to repeatedly demonstrate a blunted dopamine response to amphetamine administration in individuals chronically using drugs of abuse²⁴⁻²⁷. However, BP measures assume steady-state radioligand binding, and thus steady-state neurotransmitter levels, for the scan duration.

Page 10 of 51

This assumption works well with amphetamine because this drug induces a robust and longlived dopamine elevation that remains steady during the entire post-drug scan, allowing for reliable estimates of changes in dopamine levels with the two-scan paradigm. Other drug stimuli, such as cigarette smoking, induce short-lived neurotransmitter release that dynamically changes radioligand binding throughout the post-drug scanning period. The classic BP paradigm can underestimate or even fail to detect such transient neurotransmitter responses²⁸. Thus, **alternative analysis methods are needed to identify short-lived neurotransmitter activation with PET imaging**.

We have developed a new imaging paradigm, known as linear parametric neurotransmitter-PET (IpntPET), to explicitly accommodate time-varying changes in radioligand binding while scanning, enabling accurate detection of short-lived neurotransmitter response using PET imaging²⁹⁻³³. IpntPET identifies the spatial extent of neurotransmitter activation at the voxel level with improved sensitivity and specificity relative to two-scan paradigms^{28,34}, while also characterizing the temporal component of endogenous neurotransmitter activation^{33,34}. This approach revealed remarkable differences between men and women both in the brain areas and temporal dynamics of dopamine release in response to cigarette smoking³⁵. Importantly, these findings were consistent with men tending to smoke for the reinforcing effects of nicotine than women³⁶ (i.e., sex differences in cigarette "wanting"). However, to date lpntPET has only been used to image changes in the dopamine^{31,35} and acetylcholine³⁷ systems. Given the close interaction of the dopamine and opioid systems in the dynamics of reward processing, validating ntPET with radioligands sensitive to endorphin activation will provide powerful tools enhancing *in vivo* study of reward processes in the brain with PET imaging.

PET imaging of the opioid system has primarily been conducted with the µ-selective [¹¹C]carfentanil³⁸ and non-selective [¹¹C]diprenorphine³⁹ radioligands. Both radioligands are reported to be sensitive to endorphin levels, the opioid peptides that preferentially act at μ and δ -opioid receptors⁴⁰. Reduced [¹¹C]carfentanil binding, presumably due to increased β endorphin levels, was reported in response to acute somatic pain⁴¹⁻⁴³, affective responses¹⁸, placebo administration⁴⁴, oral amphetamine administration^{45,46}, and cigarette smoking⁴⁷. In particular, one study reported variation in average [¹¹C]carfentanil BP over time following acute somatic pain⁴² suggesting time-varying β-endorphin response to pain, albeit with biased analysis methods. These initial reports suggest that [¹¹C]carfentanil is a suitable radioligand to detect short-lived changes in β -endorphin levels. Moreover, increasing interest in marijuana's diverse effects on the endogenous opioid system have identified an important role for dynorphin in potentially mediating marijuana's putative analgesic effects. The Yale PET center has developed the novel agonist radioligand [¹¹C]EKAP that exhibits kinetic properties consistent with radiotracer sensitivity to endogenous dynorphin levels. Given repeated observations of short-lived opioid peptide responses to drugs of abuse with microdialysis techniques^{48,49} (see ⁵⁰ for review), extension of the IpntPET paradigm to the opioid system could provide groundbreaking in vivo characterization of endorphin release following drug stimulus.

Page 11 of 51

In the current proposal we propose to image the dopaminergic and the opioidergic response to drugs of abuse in the same subjects. Thus, we will be able to potentially visualize multiple neurotransmitter systems within the same person and we will be able to compare the neurotransmitter system map between drugs of abuse.

3. **Research Plan:** Summarize the study design and research procedures using non-technical language that can be readily understood by someone outside the discipline. **Be sure to distinguish between standard of care vs. research procedures when applicable, and include any flowcharts of visits specifying their individual times and lengths. Describe the setting in which the research will take place.**

3.1 Overall Research Design:

This study will recruit drug users (tobacco or marijuana) to participate in one magnetic resonance imaging scan (MRI),one [¹¹C]raclopride PET scan, two [¹¹C]carfentanil PET scans, and two[¹¹C]EKAP PET scans (for marijuana users/marijuana exposed). If subjects have never been in a PET scanner, they may participate in a brief "mock" PET scan session prior to their actual scan to familiarize them with the environment (reduce the novelty) and if they are a smoker, to familiarize them with the mechanics of smoking in the scanner.

Aim 1. To examine the magnitude, location and timing of drug-induced dopamine release.

- **a.** Tobacco smokers (n=20) will be imaged with [¹¹C]raclopride PET, after overnight abstinence from tobacco smoking. Subjects will smoke their preferred brand of cigarette during the PET scan.
- **b.** Marijuana smokers (n=20) will be imaged with [¹¹C]raclopride PET, after overnight abstinence from marijuana smoking. Subjects will smoke a marijuana cigarette during the PET scan.

Aim 2. To examine the magnitude, location and timing of drug-induced beta-endorphin release. *We will attempt to use the same subjects from Aim 1 for Aim 2. (Marijuana Exposed Healthy Controls are the exception)

- **a.** Tobacco smokers (n=20) will be imaged with [¹¹C]carfentanil PET, after overnight abstinence from tobacco smoking. Subjects will smoke their preferred brand of cigarette before or during the drug condition PET scan
- **b.** Marijuana smokers and Marijuana Exposed Healthy Controls (n=20) will be imaged with [¹¹C]carfentanil PET, after overnight abstinence from marijuana smoking. Subjects will smoke a marijuana cigarette before or during the drug condition PET scan.

Aim 3: To examine the magnitude, location and timing of marijuana-induced dynorphin release. Cannabis has diverse effects on the endogenous opioid system. We will image Marijuana Smokers and Marijuana Exposed Healthy Controls (n=20) with [¹¹C]EKAP PET, after overnight abstinence from marijuana smoking. Subjects will smoke a marijuana cigarette before or during the drug condition PET scan. For Aim 1 using a single scan paradigm, drugs will be administered beginning approximately 35 minutes after the radiotracer injection, as previously validated³⁵. For Aim 2 and 3, since this approach has not yet been done in people with [¹¹C]carfentanil or [¹¹C]EKAP, we will use a two scan paradigm (baseline and challenge). Drugs will be administered either before (approximately 15 min prior to radiotracer injection) or during (30-60 minutes after radiotracer injection) drug condition PET scan, which may occur after a baseline condition PET scan. The scans will be analyzed to produce the magnitude *and* temporal characteristics of the DA and beta-endorphin signature of drug use under each condition.

3.2 Subject Selection:

All research subjects will be recruited under guidelines of the Yale University Institutional Review Board (Human Investigation Committee). Subjects will be recruited from the community at large via IRB-approved advertising (television, newspaper, postings in community locations, Craigslist, Facebook).

Screening Evaluation

Potentially eligible subjects will undergo an initial screening evaluation within 6 months of PET scanning. The purpose of this evaluation is to ensure that subjects meet study criteria. After informed consent is obtained, a medical history, vital signs, physical examination, and EKG will be performed. Several laboratory tests will be performed at this visit, which may include a complete blood count (CBC), chemistry profile, thyroid function studies, serum ß-HCG (women only), urinalysis, and urine toxicology screen. All female subjects will undergo a pregnancy test at the time of screening. Additionally, urine pregnancy tests will be done on the day of each PET scan before radiotracer injection. Urine drug screens will be done at intake and on PET days.

3.3 Assessments:

All participants will be screened initially using a telephone screen that will include questions to evaluate medical history, personal and familial psychiatric and smoking history. A wide range of measures, such as psychiatric and substance abuse history, medical assessments and affective symptoms will be measured during the intake evaluation.

3.3a. General Intake Assessments

1. Demographic Questionnaire This questionnaire will obtain: (1) basic demographic information including age, gender, marital status, employment status, occupation, (2) alcohol/drug history, (3) family history of alcohol/drug use, depression, anxiety, and smoking history.

2. Medical History This questionnaire will obtain a basic medical history (personal and family) including past or current conditions such as neurological, endocrine, cardiovascular, renal, liver, and thyroid pathology. Current body weight and current medications will also be assessed.

3. Medical Assessments will include a physical exam by a state licensed physician, an EKG, and laboratory tests which may include a complete blood count, blood urea nitrogen, creatinine, fasting blood sugar, electrolytes, liver function tests, thyroid function tests (including T_3 , T_4 , T_3 RU, estimated free T4), thyroid stimulating hormone levels, urine toxicology, and urinalysis. Female subjects will have serum pregnancy tests.

4. Illicit Drug/Pregnancy Screen A urine sample may be collected to determine current illicit drug use (for all potential subjects). In addition, serum samples will be collected at the intake

Page 13 of 51

visit and urine samples will be collected on each PET scan day to confirm that the subject is not pregnant.

5. Structured Clinical Interview for DSM-IV Axis I Disorders The psychotic screening and depression sections of the Structured Clinical Interview for DSM-IV Axis I Disorders (SCID) will be used to determine whether subjects meet exclusion criteria for diagnosis of significant psychopathology such as schizophrenia and bipolar disorder ³⁸.

6. Columbia Suicide Severity Rating Scale (C-SSRS). The C-SSRS is designed to measure suicidal ideation (50).

7. Multidimensional Scale of Perceived Social Support (MSPSS) is a brief research tool designed to measure perceptions of support from 3 sources: Family, Friends, and a Significant Other.

8. Barratt Simplified Measure of Social Status (BSMSS) is a measure of socio-economic status.

3.3.b. Mood Measures

We will obtain these measures at intake and also on the PET scan day.

1. Center for Epidemiological Studies Depression Scale (CES-D) The CES-D³⁹ is a 20-item self-report instrument, which has been extensively used in both clinical and nonclinical populations to measure the frequency and severity of depressive symptoms over the past week. The CES-D, which has been used to document the severity of depressive symptoms in adults and has been shown to be a sensitive measure of negative affect in smokers, will be used in the proposed studies to measure levels of mild depressive symptoms.

2. Anxiety: The State-Trait Anxiety Inventory⁴⁰ is a 40-item, self-report measure, comprised of two subscales. The State-Anxiety scale is 20 items and assesses transitory states characterized by feelings of tension, apprehension, and heightened autonomic reactivity. The Trait-Anxiety scale is 20 items and assesses stable individual differences in anxiety proneness.

3. Impulsivity: Barratt Impulsiveness Scale (BIS; ⁵¹) is a 30 item self-report instrument designed to assess the personality/behavioral construct of impulsiveness.

4. Beck Depression Inventory: This widely used 21 item self-report instrument will be used to assess depressive symptomatology in addition to the SCID (43).

3.3.c. Smoking and other Drug Measures

We may obtain these measures at intake and also on the PET scan day.

1.Fagerstrom Test for Nicotine Dependence (FTND). This will be used to measure the severity of nicotine dependence. It is a 6-item scale with an internal consistency of .61 and its total score is closely related to biochemical measures of intensity of smoking. A score of at least 3 is necessary for inclusion in the study.

2. Smoking History. This questionnaire will assess basic smoking status and history such as number of years smoked, number and length of quit attempts, reasons for quitting, and second hand smoke exposure.

3. Nicotine Withdrawal Checklist. This measures the severity of eight withdrawal symptoms on 5-point Likert scales.

4. Tiffany Questionnaire of Smoking Urges (QSU). The QSU-brief is a 10-item questionnaire that evaluates the structure and function of smoking urges. Subjects indicate on a likert-type scale how strongly they agree or disagree with each statement with a score of 1 (strongly agree)

Page 14 of 51

to 7 (strongly disagree). This characterizes 'urges to smoke' into a negative affect related to relief of withdrawal symptoms and positive affect related to expectancy of reinforcement. 5. Wisconsin Predicting Patients' Relapse Questionnaire (WI-PREPARE). A brief, 7-item questionnaire that predicts relapse rate (49).

6. Timeline Followback for alcohol, tobacco, and illicit drugs. Questionnaire to measure the amount of alcohol, tobacco, and other drugs that have been used in the past 30 days.

7. Visual Analog Scale (VAS) self ratings for drug effects. Subjects will answer questions to assess behavioral changes induced by substance use.

8. Cannabis Problems Questionnaire is a 22 item self-report instrument to document cannabisrelated problems.

9. Marijuana Motives Questionnaire is a 25 item self-report instrument to characterize individual's motivations for using marijuana.

10. Marijuana Smoking History Questionnaire is a 23 item self-report instrument to characterize the dose and frequency of marijuana use and quit attempts, both over lifetime and the past 30 days.

11. Marijuana Craving Questionnaire is a 12 item self-report instrument to document marijuana craving.

12. Cannabis Withdrawal Scale is a 19 item self-report questionnaire to document symptoms of cannabis withdrawal.

13. Clinician Administered Dissociative Symptoms Scale is a 27 item instrument administered by trained research staff to characterize present-state dissociative symptoms.

3.3.d. Cognitive Measures

We may obtain these measures at baseline and up to two times on the PET day.

1. Cogstate Battery (30 minutes) – This computerized test battery will assess memory and cognition. The tasks may include:

a. International Shopping List Task – a computerized task to assess verbal learning and memory.

b. Groton Maze Learning Task – a computerized task to assess executive function and spatial problem solving.

c. Detection Task – a computerized task to assess psychomotor function and speed of processing.

d. Identification Task – a computerized task to assess visual attention and vigilance.

e. One Card Learning Task – a computerized task to assess visual learning and memory.

f. One Back Task and Two Back Task – computerized tasks to assess attention and working memory.

Probabilistic Reward Task (PRT) – The PRT has been successfully used to assess reward responsiveness (51-53). In each trial, subjects choose which of two difficult-to-differentiate stimuli was presented. Stimuli consist of simple cartoon faces (diameter: 25 mm; eyes: 7 mm) presented in the center of the monitor. At the beginning of the trial, the face has no mouth. After a given delay, either a straight mouth of 11.5 mm ("short mouth") or 13 mm ("long mouth") is presented for 100 ms. Subjects are instructed to press an appropriate button to decide whether a long or small mouth had been presented. Unbeknownst to subjects, correct identification of one stimulus

Page 15 of 51

("rich stimulus") is rewarded three times more frequently (*"Correct! You won 20 cents"*) than the other ("lean") stimulus. In healthy controls, this reinforcement schedule leads to a response bias (i.e., a preference for the more frequently rewarded stimulus). The degree of response bias toward the more frequently reinforced alternative will be used for operationalizing sensitivity to reward.

Cold Pressor Task

Subjects may be asked to participate in the Cold Pressor Task. The cold pressor task (CPT) is a stress task used to measure pain sensitivity and pain tolerance. This task will be used to determine alterations in pain thresholds as a result of substance use. Participants will immerse their hand (up to the wrist) for up to 5 minutes in the experimental (ice-cold temperature 0-4°C)) and control (room temperature (20°C)) conditions. Physiological measure (heart rate, blood pressure and subject responses (stress, mood) will be collected 5 minutes before, 1 minute into, and immediately after the CPT.

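### Could the unscheduled cold pressor task distort the comparison of the two carfentanil scans?

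*Combined protocol and SAP*

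**What the plan says.** The Cold Pressor Task appears as an unnumbered subheading at the end of Section IV.3.3.d (Cognitive Measures). Subjects may be asked to hold a hand in water at 0-4°C for up to 5 minutes, with room-temperature water as the control condition. The stated purpose is: "This task will be used to determine alterations in pain thresholds as a result of substance use". The only timing in that paragraph concerns the readings around the immersion: "5 minutes before, 1 minute into, and immediately after the CPT". The sentence opening Section IV.3.3.d says "We may obtain these measures at baseline and up to two times on the PET day"; it is not certain that it governs the task. Section IX.2 pays per occasion, so repeat runs are foreseen.

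For Aims 2 and 3, Section IV.3.1 says "we will use a two scan paradigm (baseline and challenge" scans, and smoking takes place before or during the "drug condition PET scan, which may occur after a baseline condition PET scan". Under PET Scans in Section IV.3.4, only scans with different tracers must fall on different days, so both carfentanil scans may share a day.

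The Background (Section IV.2) says that lower carfentanil binding, put down to raised endorphin "levels, was reported in response to acute somatic pain". It adds that one pain study saw binding change over time, and that carfentanil "is a suitable radioligand to detect short-lived changes in" beta-endorphin.

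**The concern.** Pain and smoking would act on carfentanil binding in the same direction. If a subject did the ice-water task shortly before one carfentanil scan and not the other, any pain effect still present would enter the difference between the scans and look like a drug effect, or hide one. The task's purpose makes a before-and-after-smoking schedule a natural choice. Because scans are acquired at rest, a pre-smoking run on a challenge day would probably come before the challenge scan. If both scans share a day, a run could also fall between them. The protocol does place another side measure, the Cigarette Evaluation Scale, straight after the scan, so the silence here stands out. At stake would be the Aim 2 estimate of beta-endorphin release and, through the same two-scan design, possibly the dynorphin estimate in Aim 3.

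**Working it through.** The plan states no figure for this point, so the check covers the direction of the bias, the conditions it needs, and the cost of the obvious remedy.

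**Direction.** Let B be the true baseline binding potential, D the true fall due to the drug, and Pb and Pc the pain-related falls still present in the baseline and challenge scans. With the contrast described in the Background (baseline minus post-drug):

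(B − Pb) − (B − D − Pc) = D + (Pc − Pb)

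| Placement of the task | Measured change |
|---|---|
| Effect reaches the challenge scan only | D + Pc (overstated) |
| Effect reaches the baseline scan only | D − Pb (understated) |
| Effect equal in both scans | D |
| After the last scan, on a day without the tracer, or effect faded before the scan | D |

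The documents give neither size nor duration for Pb or Pc, so nothing beyond the sign can be derived, and the sign depends on a schedule that is not written down.

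**Conditions.** All of the following must hold for the bias to arise:

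1. The optional task is used in that subject.
2. It is used on a carfentanil day. The Section IV.3.3.d sentence would allow this if it applies, but no text says so. Section IV.3.4 also says that ratings are obtained at screening, which is not conclusive for this task.
3. The run falls before or between the scans.
4. It is not matched across the two scans.
5. Its effect lasts into a scan.
6. The result is read as a difference between the two scans.

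On condition 5, the Background describes a time-varying response to pain, and nothing in the documents describes persistence after a brief stimulus. It also warns that the "classic BP paradigm can underestimate or even fail to detect such transient neurotransmitter" responses, so even a residual effect might register weakly in a conventional binding comparison.

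On condition 6, the test set out in Section IV.12 is an F-test of lp-ntPET against MRTM on model fit, not a between-scan difference. Data Processing in Section IV.3.4 names lp-ntPET and voxelwise analysis. No section says how the two carfentanil scans are compared.

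**Cost of requiring the task after scanning.** Smoking is about 15 minutes before injection, or 30 to 60 minutes after it (Section IV.3.1); a scan lasts up to 120 minutes (Section IV.3.4). The delay from smoking to the end of a full-length scan is:

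- smoking 15 minutes before injection: 15 + 120 = 135 minutes
- smoking 30 minutes after injection: 120 − 30 = 90 minutes
- smoking 60 minutes after injection: 120 − 60 = 60 minutes

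Shorter scans reduce these delays. Moving the pre-smoking run also has drawbacks. Intake does not give tobacco smokers an abstinent value: Section IV.7 requires carbon monoxide above 10 ppm at intake, whereas Section IV.3.4 takes a reading below 11 ppm as the sign of abstinence on scan days. Moving it to an EKAP day would shift the same question to another opioid tracer with the same two-scan design, on a day when a radial artery line stays in place and the task immerses the hand to the wrist.

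**The case for a change.** The best case for acting is that the omission is real, the mechanism is the protocol's own, and prevention would take one sentence. The protocol already accepts that order and state can affect a scan: it justifies the mock sessions partly as a way to reduce order effects from anxiety or expectation. The task is described as a stress task as well as a pain measure. If every subject did it on the same unmatched schedule, pain and drug effects could not be separated afterwards.

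Part of this stands. The order is not stated, and the shared direction is correctly read from the Background. The warning about binding-potential methods also shows only that a transient effect may be missed, not that it is absent.

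The rest is weaker. Because the task is optional, subjects who skip it would give some comparison, though not a randomised one. The one-sentence remedy is not free: it delays the pain measure that the task exists to provide. A sensitivity analysis that drops only the affected scan would leave that subject with no baseline-challenge contrast; the whole pair would have to be set aside. The Cogstate battery and the Probabilistic Reward Task, in the same section, also have no stated position relative to the scans, which suggests that the protocol treats such detail as a matter for the visit schedule.

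**Conclusion.** No change to the plan is needed. The protocol leaves the order of an optional side task unwritten; it does not prescribe an order that gives a wrong result. The possible bias equals the difference in residual pain effect between the two scans. It could go either way, cannot be sized from the documents, and is zero if the task is run after scanning, is matched across the scans, or has an effect that fades before the next scan. Fixing the order in the protocol would exchange this undemonstrated bias for a pain measure taken about 60 to 135 minutes after smoking with a full-length scan, which may miss the early effect. Either choice is defensible.

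The conclusion assumes that study staff, knowing the Background evidence on pain and carfentanil, will not routinely put an ice-water immersion just before one scan of a pair, and that an analyst who finds such a run will consider that subject's pair separately. It would change if the working visit schedule placed the task before only one of the paired opioid-tracer scans, or if there were evidence that the pain response lasts into a later scan. The documents show neither.
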